2.2.2 Procedures

2.2.2.1: Eligibility screening and inclusion in the study:

Study participants will be selected from patients in regularly follow-up at UZ Gent. Screening evaluation will be performed prior to study entry. The patient will be invited to participate in the trial and provided information about the aims and risks of the project. After obtaining written informed consent, clinical eligibility will be assessed. Patients will be eligible for enrolment if they fulfil all the inclusion criteria. Patients will not be eligible for the study if they meet any of the above described exclusion criteria. If patients are not on an integrase inhibitor based regimen, they should be switched 3 months prior to study initiation.

The following will be assessed at this visit:

- Assessment of subject eligibility according to the inclusion and exclusion criteria
- Demographic and epidemiological data
- Medical history (past and current), including HIV-associated conditions
- Full antiretroviral history (including result of resistance assays if available)
- Review of non-antiretroviral medication within the last 30 days with special attention for immunomodulatory and immunosuppressive drugs and anticoagulation therapy.
- Physical examination including vital parameters, height and weight
- HIV viral load and CD4 T cell count.
- Laboratory test (non-fasting): hemoglobin, absolute neutrophil count (ANC), platelets, creatinine, electrolytes, liver enzymes AST & ALT, coagulation. Hepatitis HCV & HBV serology if necessary.
- Pregnancy test among women.
- ECG and lung X-ray
- assessment of good peripheral venous access

2.2.2.2: In depth sampling:

An in depth sampling will be planned before therapy interruption. Together with our collaborators we will put in place a standardised trajectory, aiming for the highest possible comfort for the participants. The patients will therefore be admitted in the hospital for 24h. Bronchoscopy, gastroscopy and coloscopy will be performed under anaesthesia. Before the anaesthesia, the anaesthesiologist will perform a lumbar puncture. During anaesthesia a bone marrow aspirate and an inguinal biopsy will also be effectuated. Leucapheresis can be organised on ambulatory basis within one month of the in depth sampling but not the day before or after due to increased bleeding risk. If leucapheresis is contra-indicated this will be replaced by a peripheral blood draw of 6x 9ml. Sperm collection will be done by standardised

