protocol of the fertility clinic. Vaginal lavage will be done during hospitalisation or ambulatory at the gynaecology consultation.

2.2.2.3: Treatment interruption to allow viral rebound and subsequent sampling:

A second sampling will be foreseen after therapy-stop once viral rebound is detected and will consist on leukapheresis (or peripheral blood draw if contraindicated), lumbar puncture and genital sampling. As before there should be a timespan of minimum 24h between leukapheresis and puncture due to increased bleeding risk. For this sampling an overnight stay in the hospital will be arranged.

After the treatment interruption is initiated a follow-up of plasma viral load will be organized. Patients will be stopped at D1 (Friday) and a first control will be performed D4 (Monday) and D7 (Thursday). On an average we expect people to have rebounded before D12 and the second sampling will be planned like this. If the viral load control on D11 shows no signs of rebound, sampling will be postponed and further follow-up will be organized. If after 3 weeks the patient has not rebounded, we will discuss this result with the patient and we will propose weekly controls of viral loads and restart therapy after 2-3 months, after the second sampling. For patients without detectable viral load after 1 month, an additional sampling at that point (blood sampling, lumbar puncture and genital sampling) will be proposed.

Sampling will consist of

a: Leukapheresis

Participants will undergo leukapheresis at the Ghent University Hospital. Leukapheresis runs will last approximately three hours for the collection of $> 1 \times 10^8$ cells Peripheral Blood Mononuclear Cells. Leukapheresis is considered the gold-standard method for obtaining large volumes of peripheral cells from HIV-infected patients, and has been performed safely in individuals with and without hematologic malignancy and/or HSCT (1). Leukapheresis will be performed twice for each participant, with a minimum of three months interval following the initial collection. If contra-indicated this procedure will be replaced by a peripheral blood draw of 6x9ml.

b: Bronchial lavage and endobronchial ultrasounds guided sampling

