It might be important to approach the central nervous system differently compared to the other compartments for two reasons. First, due to the blood-brain barrier this reservoir might be more compartmentalized and secondly tissue sampling is not realistic. Most probably we will not be able to perform phylogenetic analysis on the lumbar fluid in patients on cART due to limited input material. Therefore, we will evaluate this reservoir mainly quantitatively in terms of viral rebound dynamics in the cerebrospinal fluid (CSF) compared to rebound in the peripheral blood (at day 12). An earlier or higher viral rebound in the CSF would then indicate that the replication competent reservoir is likely contained within the brain.

2.3.3 Quantitative assessment of the HIV-1 viral reservoir in the plasma and in different cellular fractions of the different anatomical sites.

To identify the nature of the replication competent HIV-1 reservoir (active cryptic replication versus dormant HIV-1 DNA) we will further characterize the viral reservoir in the body compartments containing viral DNA that is most closely related to the rebounding virus. The cell populations, sorted from the different tissues will be evaluated using a set of viral reservoir assays based on HIV-1 RNA/DNA intermediates, formed during each step of the replication cycle. The assays have been translated by my group from in vitro research towards the clinic, using state of the art droplet digital PCR technology, allowing absolute ultrasensitive quantification. The cellular blood fractions and cellular fractions from the anatomical compartments will be separated and subjected to quantification of cell-associated RNA, total HIV-1 DNA and 2 LTR circular HIV-1 DNA.

- Our data show that HIV-1 is present in different anatomical compartments throughout the body. We will perform total HIV-1 DNA quantification on the different cellular fractions to understand the size of the potential reservoir in the different compartments. Furthermore, we will evaluate a potential correlation of the size of total HIV-1 DNA in the cellular compartment with the identified source of rebound.

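### On the expected pathway the only off-therapy CSF sample follows detected plasma rebound, so an earlier CSF rebound is not directly observed and a higher CSF level alone does not show a brain source

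*Combined protocol and SAP*

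**What the plan says.** The CNS paragraph of section 2.3.2 treats this compartment differently from the others. It gives the reason: "Most probably we will not be able to perform phylogenetic analysis on the lumbar fluid in patients on cART due to limited input material". The compartment is therefore to be evaluated "mainly quantitatively in terms of viral rebound dynamics in the cerebrospinal fluid (CSF) compared to rebound in the peripheral blood (at day 12"), and the reading is fixed in advance: "An earlier or higher viral rebound in the CSF would then indicate that the replication competent reservoir is likely contained within the brain".

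The sampling that feeds this rule is described elsewhere in the protocol:

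- **First puncture, on therapy.** Section 2.2.2.2 places it in the in-depth sampling before the interruption: "Before the anaesthesia, the anaesthesiologist will perform a lumbar puncture". Section 5 puts the interruption about 3 months later.
- **Plasma follow-up.** Section 2.2.2.3: "Patients will be stopped at D1 (Friday) and a first control will be performed D4 (Monday) and D7 (Thursday"). A further control falls on D11.
- **Second puncture.** Section 2.2.2.3: "A second sampling will be foreseen after therapy-stop once viral rebound is detected and will consist on leukapheresis", with a lumbar puncture and genital sampling in the same set. On timing: "On an average we expect people to have rebounded before D12 and the second sampling will be planned like this". And: "If the viral load control on D11 shows no signs of rebound, sampling will be postponed".
- **Afterwards.** Section 5 has therapy restarted after this sampling.
- **Exceptions.** Section 2.2.2.3 proposes an extra puncture to patients with no detectable viral load after 1 month. For patients without rebound after 3 weeks, it proposes weekly controls and a restart after 2-3 months, following the second sampling.

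**The concern.** The rule has two limbs, earlier and higher, and either one is enough for a brain-reservoir reading. For the participants whom the plan expects to be typical, the schedule supplies repeated plasma values but one off-therapy CSF value, and that value is conditional on plasma already being positive. The pattern that would show CSF-first directly (CSF positive, plasma undetectable) cannot arise on that pathway. The remaining limb, a higher level, can be measured but does not identify where the virus came from.

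At stake is how the CNS result is reported. Other compartments are judged by linking their sequences to the rebounding virus. The CNS could receive a positive attribution from a single paired level described as dynamics. With 10 participants and the reliance on individual results stated in section 4.3, one such reading could colour the conclusion on the study's main goal.

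**Working it through.** The plan gives no calculated figure for the CSF comparison, so there is none to reproduce. The check is on what the schedule allows to be observed.

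**Inputs.** Stop on D1; plasma controls on D4, D7 and D11; second sampling planned around D12 (section 2.2.2.3); comparison at day 12 (section 2.3.2); two punctures per participant (section 2.2.2.3, item g), the first on therapy.

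**Step 1: off-therapy values by D12.** Plasma: 3 scheduled controls. CSF: 2 punctures − 1 on therapy = 1. One point has no slope, so no rebound dynamics can be estimated in CSF.

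**Step 2: onset windows.** Plasma onset lies between the last undetectable and the first detectable control. CSF onset, if CSF is positive, lies at best between the stop and the puncture. *At best* is needed because the on-therapy CSF value is about 3 months old at the stop.

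| First positive plasma control | Plasma window | CSF window, puncture on D12 | Ratio |
|---|---|---|---|
| D4 | D1 to D4, 3 days | D1 to D12, 11 days | 11/3 = 3.7 |
| D7 | D4 to D7, 3 days | D1 to D12, 11 days | 11/3 = 3.7 |
| D11 | D7 to D11, 4 days | D1 to D12, 11 days | 11/4 = 2.8 |

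In each row the plasma window lies wholly inside the CSF window, so either order remains possible.

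**Step 3: other puncture days.** Let P be any puncture day at or after the participant's first positive plasma control. That participant's own plasma window ends on or before P, so it lies inside D1 to P. The ratios do depend on P. If the text allowed a D8 puncture after a positive D7 control, the ratio would be 7/3 = 2.3. If sampling is postponed, the CSF window lengthens while plasma is still checked 2-3 times a week to week 4 and weekly afterwards.

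**Step 4: what a level says about order.** Assume exponential growth from 20 copies/ml, which is the plasma limit in section 2.1.2 and is only assumed for CSF. With level L on D12 and doubling time Td, the crossing day is 12 − Td × log2(L/20). The levels and doubling times below are assumptions; the documents give none.

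- CSF at 1,000 with Td 0.75 days: 12 − 0.75 × 5.64 = D7.8. Plasma at 500 with Td 1.5 days: 12 − 1.5 × 4.64 = D5.0. CSF is higher but later.
- With equal doubling times, the higher level always crosses first.
- Plasma undetectable on D7 and CSF at 1,000 on D12: CSF onset falls after D7 only if Td < 5/5.64 = 0.89 days. At 10,000 the bound is 5/8.97 = 0.56 days.

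Order can therefore be inferred from a level, but only through a stated assumption on growth.

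**Step 5: how often the exception could help.** Let p be the probability of no detectable viral load at 1 month. The documents give no value. For p from 2% to 20%, the expected number is 10p = 0.2 to 2.0 participants, and the chance of at least one is 1 − (1 − p)^10 = 18% to 89%. Refusal would lower this.

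**The case against.** The strongest reply is that the plan is more modest than it looks. It names one comparison day, so a single paired comparison may be what is meant, and *earlier* and *dynamics* may be loose wording. The conclusion is only called likely. Sequencing is ruled out only for CSF on therapy, which leaves room for rebound CSF. The CSF comparison is not listed separately among the outcomes in section 2.2.1. The 1-month puncture could show CSF-first directly.

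Much of this stands, and it keeps the point narrow. It does not rescue the rule. Hedging expresses confidence but does not make an unobserved order observable. The 1-month puncture is offered only to patients outside the expected course, and section 3.1 lets patients refuse a procedure.

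Some stronger readings are tempting but not supported:

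- A reader might infer that two positive samples say nothing about order. Step 4 shows that a bound on growth can inform it.
- A reader might take the ratio of 2.8 to 3.7 as general. It holds for a D12 puncture only, and it compares window widths. It does not measure an effect on any reported result.
- A reader might infer that the study cannot identify the source of rebound. Linking tissue sequences to rebound plasma does not depend on the CSF rule.
- A reader might treat the non-specificity of a higher level as an established finding. It is a logical alternative, and the documents give no CSF RNA figure from which to size it.

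**Conclusion.** The concern holds in a limited form. On the expected pathway, an earlier CSF rebound is not directly observed, dynamics cannot be estimated from one off-therapy value, and a higher CSF level alone does not separate a CNS source from blood-derived virus growing faster there. For a D12 puncture, CSF onset is bracketed to 11 days at best, against 3 or 4 days for plasma. The containment holds for any puncture that follows the participant's first positive plasma control.

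The limitation is asymmetric. A negative CSF with positive plasma can argue against CSF-first, but the expected schedule cannot directly demonstrate CSF-first. Only a puncture made while plasma is undetectable could do so: the proposed 1-month sampling, or a second sampling without rebound.

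Confidence is high for the schedule argument. The argument about source is reasoning, not a documented figure. All of this rests on the text, because the flowchart in section 2.2.3 and a figure after the lumbar-puncture text are not shown. The CNS rule should be corrected; the sampling schedule need not change for that.

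**What to change.** In section 2.3.2, for samples triggered by plasma rebound, replace the earlier-rebound criterion and the reference to dynamics with a descriptive, per-patient CSF and plasma HIV RNA level at one time. Show it beside the on-therapy CSF RNA. State that a higher CSF level alone is not read as a brain reservoir.

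State the readings in advance, there and in section 4.3:

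- **Both positive:** order not directly observed. Any inference is a sensitivity analysis under a stated bound on growth rate.
- **CSF negative, plasma positive:** argues against CSF-first, subject to a stated CSF detection limit.
- **CSF positive, plasma undetectable:** compatible with CSF-first only if pre-interruption CSF RNA was undetectable and the CSF and plasma detection limits are comparable. Note the gap of about 3 months before the stop, during which CSF virus could have appeared on therapy.
- **Either CSF sample missing:** no statement that CSF rebounded before plasma.

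Where rebound CSF yields enough RNA, apply the single-genome and phylogenetic methods of section 2.3.2 to it. Compare it with rebound plasma and any pre-interruption sequences, few or none of which are expected from CSF. Otherwise report the CNS result as indeterminate.

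Reconcile the statement in section 2.2.2.3, item g, that each participant has two punctures with the additional 1-month puncture in the same section.

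**Cost.** Mostly wording. There is some added assay work: RNA in the on-therapy CSF if not already intended, and sequencing of rebound CSF, which may fail. Both draw on CSF already collected, at most 3-5 ml per puncture and shared with the assays of section 2.3.7. The CNS claim becomes weaker and some participants will be reported as indeterminate.

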3.1 Risks

In this project proposal, we have two important (risk related) ethical questions:

- 1) Is it safe to select "healthy volunteers (seropositive people with a normal life)" and
- 2) Can a treatment stop be carried out safely?

These two questions will be further addressed in this document. Informed consent will be obtained from each eligible subject prior to each procedure and study staff will transport all material for immediate processing at the HIV research virology laboratory. Patients may refuse a procedure, but remain enrolled in the study and undergo other tissue sampling, and/or analytical treatment interruption.

3.1.1 Risks related to patient sampling

For all individual procedures, the individual risk will be discussed with the patient by an open communication. For each procedure, the reported individual risks are low (typically 1/1000 for adverse events in all procedures), and are based on data from sick patients (e.g. lung disease for which bronchoscopy is needed). Also the patient's cumulative risk (all procedures taken together) will be discussed extensively. Risk estimation per procedure is shown below.

Endobronchial ultrasound guided lymph node biopsy (EBUS) is considered a safe procedure (Rintoul RC et al. Thorax, 2014). A retrospective analysis involving 16.181 patients, reported 23 serious adverse events (SAE) (0.14%) and 35 adverse events (AE) (by 0.22%) and no mortality. With EBUS, infectious SAE were most prevalent (down 0.07%), especially in patients with cystic lesions and sarcoidosis.

Limited data is available for bronchoalveolar lavage (BAL) in patients with no existing pulmonary disease, and this technique is considered to be safe in healthy subjects. In the case of extensive lavage (immuno-BAL), in patients with severe pulmonary disease, a self-limited fever and hypoxemia are the most frequent complications (American Thoracic Society, 2012).

Bone marrow aspirate: Large data series are published from the members of the British Society of Haematologists, reporting 54 890 bone marrow samples, between 1995 and 2001

(Bain BJ Clinical and laboratory haematology (2004). 26: 315). Total of 26 AE were reported directly linked to the procedures. The most frequently reported SAE was bleeding, in 14 patients, with emergency blood transfusion in 6 patients and leading to death in 1 patient (with underlying clotting problems). The most common risk factors associated with bleeding were myeloproliferative disease, aspirin use, or both; warfarin therapy, DIC and obesity. Other adverse effects are infection, long-lasting discomfort at the biopsy site, and penetration of the sternum, which can cause heart or lung problems.

Possible complications from a lumbar puncture (LP) comprise of: local discomfort with pain at the puncture site, during or after the puncture, radicular pain, bleeding, infection and post-puncture headache. A recent review (Wright et al J Neurol 2012; 259: 1530-45) reported infections and bleeding, and each was seen in less than 0.01% of the cases. The incidence of post-puncture headache (PPH) is a fairly frequent complication and its incidence is highly dependent on the needle used. If an atraumatic needle is used, PPH is reported on average in 3-9% of the cases (Wright et al J Neurol 2012; 259: 1530-45; Lavi et al Neurology 2006; 67; 1492-1494.). All the punctures within this study will be made with an atraumatic needle. Researchers investigated the prevention of PPH in an observational study with cross-sectional data analysis (Monteiro de Almeida et al Headache 2011; 51: 1503-10). Total of 675 LPs were performed involving 477 volunteers (575 puncture in HIV-positive individuals and 100 in healthy volunteers). PPH was noted in only 0.9% of the subjects. Most cases of PPH (92%) recovered spontaneously or with medication. Three individuals were treated by an epidural blood patch. In UZ Gent an epidural blood patch is used with a protocol performed by an anaesthesiologist with specific expertise.

Biopsy of the gastrointestinal tract:

- A colonoscopy with biopsy carries a risk of bowel perforation in 1/1500. If this occurs, the perforation is recognised immediately and treated during the same endoscopy. As a result of the administration of analgesics and/or narcotic drugs other side effects can occur, such as low blood pressure, nausea, or twits. These are short-lived side effects and after a colonoscopy, the patient is kept in observation overnight, with monitoring of the pulse and blood pressure. Subjects will be counselled to avoid rectal trauma and the use of anticoagulants (e.g. aspirin, NSAIDS) before and after the procedure. Mucosal biopsies will not be taken if the participant has an increased risk for complications, including receptive anal intercourse within 3 days of the procedure, an active anal infection, or recent use of anticoagulants. Biopsies will be performed by gastroenterologists who have training and clinical certification in coloscopy/ anoscopy.
- The major complication of a gastroscopy with biopsy is aspiration pneumonia (<1/1000). The risk of perforation is very small (<1/1500).

Biopsy of the lymph node: Lymfocele is the main risk in removal of lymph nodes. This complication is infrequent (<1%) and can be surgically corrected. The infectious risk is <1% and easily treatable.

Leukapheresis: is considered a safe procedure. All studies available were done in patients with hematologic or solid tumours malignancies (ex. Reik, 1997). The most frequent side effect (39%) was paresthesia due to citrate-related hypocalcaemia (1 in 10). This could easily be managed with oral calcium supplements and/ or slower flow rates. Other reactions included hypotension (4%) and headache (1,4%). Patients under antihypertensive treatment, will be asked to interrupt this treatment the day of the procedure. The bleeding risk after the procedure is transitory increased. There is also risk of catheter problems during procedure. Leukapheresis will not take place if screening beforehand reveals poor peripheral venous access or electrolyte disturbances. In these cases, the procedure will be replaced by a peripheral blood puncture (6x9ml).

Semen sample and vaginal lavage: these are non-invasive procedures and not associated with serious adverse effects.

Anaesthesia: Most healthy people don't have any problems with general anaesthesia. Although many people may have mild, temporary symptoms, general anaesthesia itself is exceptionally safe, even for the sickest patients. The risk of long-term complications, much less death, is very small. In general, the risk of complications is more closely related to the type of procedure, the general physical health, than to the anaesthesia itself. Some of the factors that can increase the risk of complications include: smoking, obstructive sleep apnoea, obesity, high blood pressure, diabetes, other medical conditions involving your heart, lungs or kidneys, medications, such as aspirin, that can increase bleeding, history of heavy alcohol use, drug allergies and history of adverse reactions to anaesthesia. Rare complications, which may occur more frequently in older adults or in people with serious medical problems, include: temporary mental confusion, lung infections, stroke, heart attack, and death.

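### The 1/1000 risk summary in section 3.1.1 is too broad for lumbar puncture and leukapheresis, and the headache figures given for the cited series cannot be reconciled as written

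*Combined protocol and SAP*

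**What the plan says.** Section 3.1 asks whether it is safe to select "healthy volunteers (seropositive people with a normal life". Section 3.1.1 begins its answer with one summary figure for sampling: for each procedure, "the reported individual risks are low (typically 1/1000 for adverse events in all procedures". It promises to discuss both individual and cumulative risk with the patient, and then announces: "Risk estimation per procedure is shown below".

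The figures that follow differ widely by procedure:

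- **EBUS.** An analysis of 16,181 patients "reported 23 serious adverse events (SAE) (0.14%) and 35 adverse events (AE) (by 0.22%) and no mortality".
- **Bone marrow.** Among 54,890 samples: "Total of 26 AE were reported directly linked to the procedures".
- **Gastrointestinal endoscopy.** Perforation at colonoscopy is 1/1500. At gastroscopy, aspiration pneumonia is below 1/1000 and perforation below 1/1500.
- **Lumbar puncture.** For infection and bleeding, "each was seen in less than 0.01% of the cases". Post-puncture headache (PPH) "is a fairly frequent complication and its incidence is highly dependent on the needle used". With the atraumatic needle, which is the one planned for every study puncture, "PPH is reported on average in 3-9% of the cases".
- **Cited PPH series.** There were 675 punctures in 477 volunteers (575 punctures in HIV-positive individuals, 100 in healthy volunteers). PPH is put at 0.9% of the subjects, 92% of PPH cases recovered spontaneously or with medication, and three people had an epidural blood patch.
- **Lymph node resection.** Lymphocele and infection are each below 1%.
- **Leukapheresis.** Paresthesia is given as 39%, with 1 in 10 in the same sentence. Hypotension is 4% and headache 1.4%.

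Section 2.2.2.3 plans leukapheresis (item a) and lumbar puncture (item g) twice for each participant.

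**The concern.** The summary speaks of adverse events, for each and all procedures, with no limit to serious ones. The EBUS paragraph directly after it separates serious from other events, so a reader has no reason to supply that limit. For lumbar puncture and leukapheresis the section's own rates are one to two orders of magnitude higher. The PPH series, which a reader could take as tempering the 3-9%, carries figures that do not fit together.

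The use of these figures is what matters. Section 3.1 requires consent before each procedure and lets a patient refuse any one of them, so rates per procedure bear on real choices. A cumulative risk built on 1/1000 would be far too low for common reactions. Section 3.1.4 itself warns that participants may give side effects too little weight. Endpoints and analyses are not touched.

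**Working it through.** **Inputs.** Rates and counts are from section 3.1.1, procedures per participant from section 2.2.2.3 (a and g), and 10 participants from section 2.1.1.

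**Step 1: reproduce the plan's own figures.**
- EBUS: 23/16,181 = 0.142% and 35/16,181 = 0.216%. These match the stated 0.14% and 0.22%.
- Cited PPH series: 575 + 100 = 675 punctures, as stated.
- Bone marrow: 26/54,890 = 0.047%, about 1 in 2,100.
- Colonoscopy perforation: 1/1500 = 0.067%.

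**Step 2: compare each rate with the summary (1/1000 = 0.1%).**

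| Event | Rate | Multiple of 0.1% |
|---|---|---|
| Puncture infection, bleeding (each) | <0.01% | <0.1 |
| Bone marrow, all linked events | 0.047% | 0.5 |
| Colonoscopy perforation | 0.067% | 0.7 |
| Gastroscopy aspiration | <0.1% | <1 |
| EBUS serious events | 0.14% | 1.4 |
| EBUS adverse events | 0.22% | 2.2 |
| PPH, cited series | 0.9% | 9 |
| PPH, atraumatic needle | 3-9% | 30-90 |
| Paresthesia, lowest reading | 0.39 × 0.10 = 3.9% | 39 |
| Paresthesia, if 1 in 10 is the incidence | 10% | 100 |
| Paresthesia, if 39% is the incidence | 39% | 390 |

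The lymph node figures (<1%) are upper bounds and decide nothing. The 4% and 1.4% for leukapheresis are left out because they may be shares of reactions and not rates per procedure.

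**Step 3: PPH over the planned punctures.** The chance of at least one PPH in two punctures is 1 − (1 − p)², assuming independence and no refusals.
- p = 0.1%: 0.2%
- p = 0.9%: 1.8%
- p = 3%: 1 − 0.97² = 5.9%
- p = 9%: 1 − 0.91² = 17.2%

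Over 10 × 2 = 20 punctures the expected number of cases is 0.02 at 1/1000, 0.18 at 0.9%, and 0.6 to 1.8 at 3-9%.

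**Step 4: can 0.9%, 92% and three describe one set of cases?** A rounded 0.9% needs a whole number k with 0.85% ≤ k/D < 0.95%.
- D = 675 punctures: k = 6 (0.89%); 7 gives 1.04%.
- D = 575 punctures in HIV-positive individuals: k = 5 (0.87%).
- D = 477 subjects: none (4 = 0.84%, 5 = 1.05%).
- D = 100 punctures in healthy volunteers: none.
- D = HIV-positive subjects: this number is not given. The 100 healthy-volunteer punctures involve between 1 and 100 people, so it lies between 477 − 100 = 377 and 477 − 1 = 476. Within that range k = 4 works for 422 to 470 subjects (4/422 = 0.948%, 4/470 = 0.851%).

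So 0.9% implies four, five or six cases. The recovery shares nearest 92% for those counts are 3/4 = 75%, 4/5 = 80%, 5/6 = 83%, or 100%. The smallest count for which any share rounds to 92% is 12 (11/12 = 91.7%), and 12/675 is already 1.8% of punctures. This conflict does not depend on the blood patches. Only on the added assumption that the three patched people are exactly the other 8% would the count be 36 to 39 (33/36 = 91.7%, 36/39 = 92.3%), or 5.3% to 5.8% of 675 punctures.

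**The case against.** The case for leaving the text alone is fair in several respects. The summary is hedged as typical and points straight to the detail. The detail is candid: PPH is called fairly frequent and paresthesia the most frequent side effect. Several procedures do fit 1/1000. The protocol commits to discussing individual and cumulative risk, to consent before each procedure and to a balanced consent form. The PPH figures stand in sequence, but the text does not say that they share one set of cases. The one largely HIV-positive series quoted gives 0.9%, well below 3-9%, and the leukapheresis data come from patients with malignancies.

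Most of this stands, and it sets the weight of the point. A reader might infer that the protocol hides the higher rates; it does not, since they follow within the same section. A reader might infer that participants are told 1/1000 in writing; the consent text is not in the documents reviewed, so that cannot be checked. What does not stand is that the hedge rescues the sentence. It covers each and all procedures and does not say serious, and even 0.9% is 9 times the figure.

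**Conclusion.** The point holds as a minor one, in two parts.

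First, the 1/1000 summary is overbroad. It is about right for the quantified serious complications of EBUS, bone marrow aspiration and endoscopy, and too high for puncture infection and bleeding. It is too low by a factor of 30 to 90 for PPH at the section's general range, and by at least 39 for paresthesia on the lowest reading. The PPH multiples need no assumption beyond the stated rates. The paresthesia multiple depends on an undefined sentence, and the per-participant figures assume independence and full attendance.

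Second, 0.9%, 92% and three blood patches cannot be reconciled as one set of cases: four to six cases against at least 12. It is tempting to conclude that one of these figures is wrong, or that giving 0.9% per subject must be a denominator error. The documents support neither. A missing source or case definition would also explain the mismatch, and 4 of 422 to 470 HIV-positive subjects would be a valid rate per subject.

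The leukapheresis sentence needs clarification; it is not a proven contradiction.

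**What to change.** In section 3.1.1:

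- Limit the 1/1000 statement to serious complications of the procedures it fits, or delete it. Say in the same place that headache after lumbar puncture and reactions to leukapheresis are much more common.
- Check 0.9%, 92% and three against the cited series, and give the source and denominator (punctures, all subjects or HIV-positive subjects) of each.
- State what 39%, 1 in 10, 4% and 1.4% each measure.
- Use the reconciled figures in the individual and cumulative risk discussion with participants, and in any written information that repeats them.

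The cost is a text edit and a look at the cited sources. The headline risk becomes less favourable, and clarifying the leukapheresis figures could move them either way. No procedure, endpoint, sample size or analysis changes.
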